- a. Approximately 500uL of plasma from the samples genotyped by CS will be tested by staff at each facility trained in the use of OLA Simple, with oversight and assistance by the [name] team over a 3-week period. The facility staff performing OLA Simple and the [name] team will be "blinded" to CS results. Results from OLA Simple will be interpreted as presence or absence of resistance using test strip lines for each codon tested, based on a visual guide for test interpretation and automated analysis from captured test images. For OLA Simple tests that show INDETERMINATE results for one or more codons, samples will be re-tested for that codon in two separate kits; if the two new results concur, that result will be used, but if the two new sets do not concur the result will be reported as a test failure for that codon. (Specimens with indeterminate or discordant results will be further analyzed as noted in "d" below.)
- b. The OLA Simple results (MUTANT, WILD-TYPE, or INDETERMINATE at each codon) will be compared to sequencing results to calculate test sensitivity, specificity, indeterminate rate, and other parameters.
- c. OLA Simple will target specific NRTI, NNRTI, and PI DRMs, including: (1) NRTI M184V/I, K65R; (2) NNRTI K103N, Y181C, G190A, V106M; and (3) PI V82A, I50V/C, I54V/M/L, I84V/A mutations (based on published analysis of DRMs among Kenyan adults in the [name] laboratory using the Illumina platform^38).
- d. Prior studies have shown that OLA Simple may be more sensitive than CS; specifically, OLA Simple can detect DRMs at ~10% of a patient's viral population while CS detects DRMs at about ~20%. To address this sensitivity gap, any sample negative for DRMs by CS but positive by OLA Simple will be tested by the more sensitive Illumina sequencing (detects DRM down to 1% of viral population, requiring as few as 2000 copies of HIV RNA). Illumina sequencing will be performed in [name] laboratory in Seattle. To avoid shipping biohazardous material, we will ship non-infectious leftover RNA from OLA Simple testing in Kisumu.

Clinical decision support for early management of children on ART: Overall, providers will be instructed to follow current Kenya National Guidelines for the management of any child with VL  $\geq$  1000 copies/mL which includes assessment of barriers to adherence and other potential factors related to virologic failure. For the intervention arm, standardized protocols and clinical decision support flow sheets will be developed to facilitate clinical management and closely record decision-making steps. Both caregivers and providers will receive POC VL results within 24 hours of the study team receiving the results. Providers will perform routine counseling and adherence intensification, then reassess VL results three months from initial VL in the intervention arm only. If DRM testing is performed, study staff will assist providers in interpreting the DRM results and assessing the need to switch to 2nd or 3rd line ART. If a provider determines a child should be switched to 2nd or 3rd line ART based on DRM testing or POC VL results, the child and caregiver will be called back within one week of VL/DRM results for counseling, adherence support, and regimen change. To facilitate caregiver response, we will sensitize patients/families on implications of VL results and provide standardized results counseling. Special consideration will be given to children newly initiating ART as they may not achieve virologic suppression after only 3 months of ART. In such cases, providers will be trained to monitor trends in VL over the first six months on ART and to consider intervention (e.g.

switch to 2nd or 3rd line) only after child has completed a minimum of 6 months on ART, unless significant primary transmitted mutations are found.

Children in the control arm will receive the SOC, which includes clinical management consistent with national guidelines including assessment of adherence and multi-disciplinary team review. Providers will follow their standard protocol for notification and follow up of children with high viral loads.

[figure not shown]

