**Oligonucleotide Ligation Assays (OLA) Simple is an extremely promising POC technology.** OLA Simple is the POC version of the “parent” lab-based OLA technology. These OLA tests overcome a major limitation of other past, failed single point mutation technologies which did not tolerate nearby polymorphisms. They hybridize well below melt temperatures, which allows tolerance to unknown variable polymorphisms. The parent, lab-based OLA has been tested in studies of pretreatment DRM in Kenya using DNA from peripheral blood mononuclear cells (PBMC). DRMs that arise during treatment failure often occur at very low levels in PBMC DNA, but at higher levels in plasma RNA; thus, the [name] lab has needed to adapt OLA Simple to test DRMs in plasma RNA. Therefore, this will be the first study to evaluate the performance of a POC DRM test using plasma RNA in treatment failure in children. Lastly, the OLA Simple has only been previously tested for codons for nucleotide reverse transcriptase inhibitors (NRTIs) and NNRTIs; the OLA Simple kit we plan to use now includes codons for protease inhibitor (PI) mutations, which has yet to be validated. The lab has developed probes for integrase strand transfer inhibitor (INSTI) DRMs (manuscript under review), so while we anticipate very few children will be on INSTI-containing ART in our study as noted above, if we find that a significant portion of the children in our study are on INSTI-containing ART, we can easily adapt the OLA Simple kits to include the relevant INSTI probes. No study to-date examines the use of a POC DRM technology to determine the minimum number of mutant codons needed to detect clinically meaningful DRMs for pretreatment or acquired DRMs in a RLS.

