We will use logistic regression models to identify risk factors associated with major and any DRMs. Potential risk factors of interest include individual-level (age, sex, duration on ART, prior antiretroviral exposure, prior viral suppression patterns, WHO clinical stage), clinical parameters (such as weight- or height-for-age), immunological status, family-level, HIV status of caregivers, socioeconomic status, and facility-level factors, such as volume of patients and urban/rural location. Covariates with p<0.20 in univariate analyses will be included in the multivariate models. We will also consider including interaction terms for any suspected effect modifiers such as age group of the child. The above analytic approaches will be taken for analyzing data from the NGS genotyping and phenotyping; in addition to descriptively generating the

patterns and distribution of NGS-detected DRM, including for minority variants and for mutations relevant to DTG, we will also compare them to the results obtained via CS when concurrent results are available.

To evaluate **Aim 2b**, CS and OLA simple-based DRM testing (Aim 4): To evaluate the test performance of OLA Simple (Aim 4a), we will compare test results for each codon from the OLA Simple test against a composite “gold standard” constructed from CS and Illumina sequencing (the latter performed on samples that are negative for DRMs by CS), stratified by retro- or prospective testing. We will calculate sensitivity, specificity, and positive and negative predictive values for the detection of DRMs per codon, organized by drug classes, for the OLA Simple. The above are the fundamental metrics the WHO, for example, considers in its prequalification application for in-vitro diagnostic and laboratory technologies approvals, achieving sensitivity and specificity >90% would demonstrate high test performance.

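### If item d governs Illumina testing and its results enter the composite reference, OLA Simple helps define its own gold standard: sensitivity cannot fall and may rise, and it is uninformative at codons with no CS-positive sample

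*Protocol*

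**What the plan says.** Two parts of the protocol describe when Illumina sequencing is used in judging OLA Simple.

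- Study methods, OLA Simple-based DRM testing, item d: "any sample negative for DRMs by CS but positive by OLA Simple will be tested by the more sensitive Illumina sequencing". Both a negative CS result and a positive OLA result are required.
- Section F, Data analysis and interpretation, Study Aim 2: the reference is a composite "constructed from CS and Illumina sequencing (the latter performed on samples that are negative for DRMs by CS"). No OLA condition is stated.

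The same analysis text plans sensitivity, specificity and predictive values "for the detection of DRMs per codon, organized by drug classes", and adds that "achieving sensitivity and specificity >90% would demonstrate high test performance". Section C.1 says the kit "now includes codons for protease inhibitor (PI) mutations, which has yet to be validated".

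Item d gives detection limits of about 20% of the viral population for CS, about 10% for OLA Simple and 1% for Illumina. Nothing states which variant share makes the OLA reference positive. The NGS thresholds listed elsewhere in Study methods belong to the dolutegravir follow-up. Nor is it said whether CS-negativity is judged per sample or per codon. The SAP has no OLA Simple section.

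**The concern.** A reference standard should not depend on the result of the test being judged. Under item d, a positive OLA result that CS does not support gets a second look by a more sensitive method and can be reclassified as a true positive. A negative OLA result that CS agrees with gets no second look, so a variant missed by both is counted as a true negative. This is discrepant resolution, and it works in the assay's favour.

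Aim 2b exists to support validation of OLA Simple, and the protocol names 90% as the mark of high performance. The effect matters most at codons with few or no CS-positive samples. These may include the protease inhibitor (PI) codons, which the protocol says still need validation.

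**Working it through.** **Plan's own base.** 284 × 0.35 = 99.4, which agrees with the stated 100 or so samples for DRM testing. The documents compute no OLA sensitivity under either rule, so there is no stated figure to reproduce for that.

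**Direction.** At one codon let
- a = CS-positive, OLA-positive
- b = CS-positive, OLA-negative
- c1 = CS-negative, OLA-positive, Illumina-positive
- d1 = CS-negative, OLA-negative, but Illumina-positive if tested

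Sens(item d) = (a + c1)/(a + b + c1)

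Sens(all CS-negatives) = (a + c1)/(a + b + c1 + d1)

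Difference = Sens(item d) × d1/(a + b + c1 + d1) ≥ 0

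The difference is above zero once there is at least one true positive and d1 > 0. This assumes the same unit (sample or codon) in both rules and a reference that is positive if either CS or Illumina is positive. A check on 200,000 random tables found no exception, including tables where a re-tested sample reveals a missed mutation at another codon. Reading one section per sample and the other per codon can reverse the direction slightly (94.7% against 94.9% in one example).

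**Inputs from the protocol** (survey table and text in section D, initial testing in C.1):
- K103N CS-positive: 46/136, about 34 per 100
- K65R CS-positive: 6/136 = 4.41 per 100
- Samples with no mutation by CS: (136 − 121)/136 = 11.0%
- PI mutations: 0 of 136
- OLA sensitivity in initial testing: 95%

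**Assumptions, not in the documents:** 10% of CS-negatives carry the variant above the reference cut-off, and OLA detects 75% of those.

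**K103N, per 100 samples.** True positives among CS-positives: 34 × 0.95 = 32.3.

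| Trigger | CS-negative | Carriers | OLA finds | Item d | All CS-negatives | Gap |
|---|---|---|---|---|---|---|
| Per sample | 11 | 1.1 | 0.825 | 33.125/34.825 = 95.1% | 33.125/35.1 = 94.4% | 0.7 |
| Per codon | 66 | 6.6 | 4.95 | 37.25/38.95 = 95.6% | 37.25/40.6 = 91.7% | 3.9 |

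Range for a carrier share of 2–15% and OLA detection of 60–90%:
- Per sample: 0.1 to 1.8 points.
- Per codon, low end (carriers 1.32, found 1.188): 33.488/35.188 − 33.488/35.32 = 0.4 points.
- Per codon, high end (carriers 9.9, found 5.94): 38.24/39.94 − 38.24/43.9 = 95.7% − 87.1% = 8.6 points.

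If OLA detects 90% of CS-positives (30.6), the per-sample figures are 31.425/34.825 = 90.2% against 31.425/35.1 = 89.5%.

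**K65R, per sample.** With a 10% carrier share: 5.016/5.237 = 95.8% against 5.016/5.512 = 91.0%, a gap of 4.8 points. If the carrier share scales with codon prevalence (10% × 6/46 = 1.3%), the gap is 0.7.

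**Codon with no CS-positive sample.** Here a = b = 0. If re-testing resolves only the discordant codon, Sens(item d) = c1/c1, which is 100%, or undefined if c1 = 0. Sequencing all CS-negatives gives c1/(c1 + d1): 0.825/1.1 = 75% under the assumptions above. The 100% needs no assumed variant share and does not depend on how well OLA performs.

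**Near-zero case.** If the cut-off sits at OLA's limit of about 10% and OLA finds nearly everything above it, d1 is close to 0 and so is the gap.

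**The case against.** The strongest reply is that there may be no contradiction. OLA-positive, CS-negative samples are a subset of CS-negative samples, item d is the operating procedure, and the analysis text may be a short description of it. That is fair, and a reader who infers a proven conflict goes further than the text allows. But if item d is the rule, the reference depends on OLA, so the problem remains.

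Second, the size rests on a variant share and detection rate that appear nowhere in the documents. This stands, so the figures above are illustrations. With about 35 K103N positives the binomial standard error at 95% is √(0.95 × 0.05/35) = 3.7 points, well above the 0.7-point gap. More stored samples from the national reference laboratory would shrink that error but not the bias.

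Third, PI use was infrequent in the survey, so trial and reference-laboratory samples may supply CS-positive PI codons. A reader should not infer that PI validation is bound to be empty.

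Fourth, item a already re-tests indeterminate codons in two kits and records a failure if they disagree. It also says that "Specimens with indeterminate or discordant results will be further analyzed as noted in" item d, and only that use in the Illumina step is open. Nothing here rests on it.

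Finally, OLA results are not returned to patients or providers, and the 90% figure is a benchmark, not a decision rule. Both are correct and limit what is at stake.

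**Conclusion.** The point holds conditionally. If item d governs and its Illumina results enter the composite, sensitivity is never lower than if all CS-negatives were sequenced, and it is higher once there is a true positive and a carrier missed by both tests. The direction needs one common unit and an either-positive reference, but no assumed rates.

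The size cannot be taken from the documents. For K103N it is about 0.7 points per sample and 3.9 per codon under the assumed inputs, and possibly near zero. It is therefore small at common codons only under the per-sample reading. A reader might infer that item d would carry a poor assay past 90%; the documents do not support that. In the base case both rules stay above 90%, and the mark is crossed only under particular assumptions.

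The firmest part is the codon with no CS-positive sample, where item d returns 100% or nothing whatever OLA's true performance, provided re-testing resolves only the discordant codon. The consequence is confined to the Aim 2b estimates; the primary outcome and patient care are not affected.

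**What to change.** 1. Reconcile item d with the analysis text so that selection for Illumina does not depend on the OLA result. Either sequence all CS-negative samples with enough RNA, or sequence all OLA-positive, CS-negative samples plus a random sample of OLA-negative, CS-negative ones, weighted in the analysis. If neither is feasible, report the OLA-triggered Illumina results descriptively and keep them out of sensitivity and specificity.
2. In every case, report the unarbitrated OLA-versus-CS table for each codon with the number of CS-positives. Give no composite sensitivity at a codon with no CS-positive unless OLA-negative, CS-negative samples were sequenced.
3. Fix in advance one variant cut-off for a positive reference call and one trigger unit, sample or codon.

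Items 2 and 3 cost only wording and tabulation. Sequencing all CS-negatives under item 1 means about 11 Illumina runs per 100 study samples on the survey figures. It means at most 24 if CS-negative means none at the OLA codons, since (136 − 103)/136 = 24.3% lacked M184V. A per-codon trigger would need far more (66 per 100 for K103N alone), which favours the weighted sample.

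No new blood is needed, since "we will ship non-infectious leftover RNA from OLA Simple testing in Kisumu". Some samples will not be evaluable, however. Illumina is described as "requiring as few as 2000 copies of HIV RNA", whereas 0.5 mL at 1000 copies/mL holds 500 copies. Reaching 2000 needs 2000/0.5 = 4000 copies/mL even before OLA uses any. The reported sensitivity may also come out lower.

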### Aim 3a: Qualitative interviews

Qualitative evaluation: We will conduct the key informant interviews (KII) with five subgroups of key informants (**Table 2**), with 10-20 KII conducted within each group with a total of 50-100 persons interviewed, some of whom will be interviewed serially up to four times during the study period, and up to 20 who have participated in Aim 3 will also fill a brief quantitative survey. We will additionally conduct up to 4 focus group discussions (FGDs) (with 6-10 participants each) with policymakers at the county or national level.

Table 2: Groups and timings of key informant interviews				
Groups	Enrollment or 3 month visit	12 month visit	24 month visit	One Time (towards the end of study period)
Group 1: Caregivers	X	X		
Group 2: Adolescents	X	X		
Group 3: Providers, lab staff and other facility staff discussing POC VL and DRM testing questions				X
Group 4: Policy makers and others discussing POC VL and DRM testing questions				X
Group 5: Providers and policy makers discussing modeling of POC VL scale up				X

*Focus group discussion guide:* Our FGD guide will be developed from an implementation science framework focusing on feasibility, acceptability, and scalability, seeking to understand how utilizing systems engineering tools would modify, support, enhance, or interfere with decision-making.

**Interview guide-** Our first KII guide will be developed from a socioecological model of pediatric viral suppression, which include individual, interpersonal, organizational, and structural/policy factors that influence pediatric viral suppression (**Figure 5**). In these KII, we will interrogate factors which acts as both facilitators and barriers to children achieving viral suppression and focus specifically on how POC VL testing and OLA Simple may improve viral suppression. We will also query participants through study visit questionnaires and in-depth interviews to understand how the novel coronavirus disease 2019 (COVID-19) has impacted intervention delivery and participants' overall well-being. In addition, we will query particular logistical aspects of optimally operationalizing POC VL testing, e.g. how caregivers prefer to learn of the results or where facility staff see the most need for POC VL testing. These logistical aspects, such as the preferred approach to delivering results, result counseling content and methods, and provider reaction to results and additional capacity building needs for the providers and health facilities, need to be explored further in order to optimize implementation and scale up of POC testing. Our second KII guide will have three phases: in phase I, each participant will be asked first to describe how they might make a decision about where to place POC VL testing machines in their geographic area. Prompts will include factors like cost, equity, coverage, competing disease priorities, and inclusion of other decision-makers. In phase

[figure not shown]
**Figure 1: Socioecological model of pediatric viral suppression**

II, each participant will be asked to look at a computer screen with the Excel-based tool from Aim 3b, be read a short set of standardized instructions, and asked to complete a series of tasks within the tool from Aim 3b. Within the tool, they will be asked to: change 1) the overall budget available to purchase POC VL machines, and 2) the maximum waiting time allowable for each sample. During this phase, policymakers will be asked to narrate their thoughts aloud, borrowing methodological approaches from cognitive interviewing, a technique used in psychology to assess comprehension. They will be asked to reflect on their experience of interacting with the tool and the interpretability of the model results. During phase III, the tool will be removed and they will be asked to describe how satisfied they felt while using the tool and how they could envision this tool being used to make decisions related to placement of POC VL machines. Of note, each interview guide for the appropriate group will be adapted for that group, e.g. the language and content of the interview guides for the adolescents may vary markedly from that we use to interview a policy maker. Following the qualitative interview, participants will complete a brief quantitative survey assessing learnability, efficiency, memorability, error recovery, and satisfaction.

### Aim 3b: Modeling

Costing and cost-effectiveness: Costing- We will use activity-based micro-costing, staff interviews, and time and motion studies, to estimate the annual cost of HIV monitoring per child living with HIV in the control (SOC) and intervention (POC VL + DRM testing and OLA Simple) arms. An experienced research assistant will conduct time and motion studies to estimate the nurse and clinician times necessary to complete the clinic visits for both arms, and to estimate the average number of patients seen in the clinic each day. We will assess the time required to complete each step of the HIV care visit (VL testing and DRM, adherence counseling). Observing multiple visits by various staff members will allow estimation of the average time taken for each step; time needed for research activities (e.g. administering informed consent) will be removed from intervention time to provide an estimate of the intervention, if implemented as a government program. For the OLA Simple testing, we will only conduct the micro-costing activities during the prospective portion of its use, as this time frame best mimics real-life use of the test and optimizes efficiency once the facility staff have gained experience conducting the tests. We will use standardized cost menus to collect site costs, including start-up costs, clinic space, human resources, supplies, and VL test costs. When data are not available from our cohort, we will utilize data from population-based studies from Kenya and sub-Saharan Africa. Additional cost data may be obtained from health facilities, published government information on labor costs, and health economics literature. Analyses will follow the guidelines for costing HIV interventions, and will reflect the provider perspective. We will also collect data on patient out-of-pocket costs to assess if POC VL testing saves participants time and expense, reflecting the societal perspective.

Mathematical model- We will parameterize a model with cost data from our microcosting activities and viral suppression data from Opt4Kids and project HIV infections, HIV-related deaths, and DALYs associated with various POC VL testing interventions. We will use EMOD-HIV, an open-source agent-based transmission model to project the cost and clinical impact of implementing POC VL testing alone and as part of a CIS in Western Kenya. EMOD includes geographic patterns of (1) age-specific demographics (fertility, mortality, migration); (2) vertical transmission, (3) a detailed, user-configurable care continuum for HIV treatment and prevention interventions that can be configured to reflect differences in treatment access and health seeking behavior among children and adolescents, including heterogeneities in access and retention in care (e.g., age and sex differences in diagnosis and linkage), and (4) a detailed within-host model of HIV progression and treatment to simulate the health and transmission effects of pediatric ART (Figure 6).

Queuing model design: Operational research models are meant to simulate the behavior of a system and use data to inform decision-making. We will use *queuing models*, a specific kind of model commonly used in industrial engineering to model waiting lines or “queues”. Queuing models represent queuing systems (i.e., waiting lines) using mathematical formulas to describe the system performance, such as average waiting time and expected queue length in the system. A queuing model has the following components; an input source generating the customer arrival process, the queue capacity, the queue discipline (e.g., first-come-first-served) and the service mechanism (e.g., number of servers, service time distribution). The queuing model example input and output parameters are delineated in Table 4, which will be collected from a representative sample of 12 clinics; we will include 5 health facilities where Opt4Kids is taking place and at 7 additional facilities selected to reflect a range of pediatric patient volumes, facility sizes, and distances to the central laboratory. To further model the parameters for a wider range of facilities in Kenya, In conjunction with our colleagues at the Kenyan Ministry of Health, we

will identify 100 facilities in Kisumu (out of ~260) that are representative of the distribution of facility sizes, locations, patient volumes, staffing and level of care, using the existing Kenyan Master Health Facility List. Lastly, we will create the Excel-based queuing model. Our objective is to identify conditions (number of POC machines in the region and the structure of hub-and-spoke or platform sharing networks) that minimize the total expected waiting time and service costs. The model will simulate various hub-and-spoke and platform sharing network configurations under a user's specification (e.g. options on entering maximum travel distance or maximum number of spoke per hub or facilities in a sharing network). For each type of facility, defined by a unique set of input parameters on sample arrival distribution and service mechanism (i.e., the type of queuing model), the model will estimate average turnaround time (including travel time) and the expected number of samples processed at each facility under a particular network structure. Using these estimates, the model will select the optimal network structure with the minimum expected cost.

